2.3 Treatment Assignment and Blinding

Approximately 30 subjects, 6 months to less than 2 years of age, will be sequentially enrolled into this study: six subjects in each cohort for Cohorts 1-3 and twelve subjects for

Part 2. Cohorts 1 to 3 will be open label with linaclotide only. Part 2 will be double blinded, and subjects will be randomized at a 1:1 ratio to linaclotide or placebo.

All cohorts will be of 7 to 12 weeks in duration: 0 to 4-week Screening Period (the minimal of 0 to 4-week period only applies to subjects that need wash out from prohibited medications), a 2 to 3-week Preintervention Period, followed by a 4-week Study Intervention Period, and a 1-week Postintervention Period.

In Part 1, linaclotide will be administered orally QD at the dose of 9 µg, 18 µg, and 36 µg for Cohort 1, Cohort 2 and Cohort 3, respectively. Part 2 will include additional subjects at the dose of linaclotide (either the 9, 18, or 36 µg dose) that exhibited the best benefit-risk profile from Part 1; and subjects receiving matching placebo.

In Cohorts 1-3, at least 5 subjects per cohort will need to complete treatment with an acceptable safety profile assessed by an internal Dose Escalation Review Committee which will give special attention to the presence of AESIs for the cohort to be declared safe to escalate to the next dose level.

In each cohort of Part 1, at least 1 subject will need to be \leq 12 months of age. The study investigator and the legally authorized representative (LAR)/parent/guardian will be given the option for the subject to continue in the next higher cohort (dose escalation) if the safety profile favors a trial cohort at a higher dose. Subjects who are participating in intrasubject dose escalation will need to repeat all screening procedures and eDiaries if > 30 days have elapsed since the subject's last dose in the previous cohort. Note: the screening number assigned by the Interactive response technology (IRT) at the initial screening visit should still be used. If symptoms have improved at the current dose level, the subject will be invited to participate in a long-term safety extension study once the study is active and accepting subjects. An internal Dose Escalation Review Committee will be monitoring the safety of Cohorts 1-3 and will provide a recommendation for the dose escalation to the next cohort or to stop the study based on the overall benefit-risk profile.

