6.2 Treatment Compliance

Treatment compliance will be summarized for the entire treatment period for the SA Population in Part 1 (by each cohort) and Part 2 (by treatment group), separately.

Treatment compliance is defined as the number of capsules actually taken by a subject divided by the number of capsules expected for the same period multiplied by 100. The number of capsules expected to be taken in a specific treatment period will be calculated by multiplying the number of days in that period by the number of capsules to be taken per day. Percent compliance will be summarized.

6.3 eDiary Compliance

An observer-reported outcome (ObsRO) instrument assessing key signs and symptoms of FC for use in children (6 months to less than 2 years of age) with FC was developed for completion by caregivers on an electronic diary (eDiary). eDiary compliance will be assessed based on the number of days with fully completed eDiary assessments by the caregiver in a specific period. The eDiary will be considered fully completed if the caregiver responded to each question in the eDiary. eDiary compliance will be summarized for the preintervention period, the open label period (Part 1), and the double-blind intervention period (Part 2), and for each week within each period based on the ITT Population.

Compliance for each subject/interval will be calculated using the following formula:

$$\text{%Compliance} = \frac{100 * \text{\# of days with completed eDiary entries within the interval}}{\text{\# of expected days within the interval}}$$

On the enrollment or randomization day, the clinic diary entry administered before the enrollment or randomization time will be included in preintervention period.

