10.4 Analysis of Vital Signs

Descriptive statistics for vital signs (i.e., temperature, body weight, height, respiratory rate, supine pulse rate, supine systolic and diastolic blood pressure) and changes from baseline values at each assessment time point will be presented by treatment group.

Vital sign values will be considered PCI if they meet both the observed-value criteria and the change-from-baseline criteria listed in Table C-4. The number and percentage of subjects with PCI postbaseline values will be tabulated by treatment group for the double-blind intervention period separately. The percentages will be calculated relative to the number of subjects with available non-PCI baseline values and at least 1 postbaseline assessment in the specific period. The numerator will be the total number of subjects with available non-PCI baseline values and at least 1 PCI postbaseline value during the specific period for the corresponding cohort. A supportive tabular display of subjects with PCI postbaseline values will be provided, including the PID number, baseline and all postbaseline (including non-PCI) values.

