10.5 Other Safety Analyses

Electrocardiogram

Descriptive statistics for ECG parameters (ventricular heart rate, RR interval, PR interval, QRS interval, QT interval, and QTc) and changes from baseline values at each assessment time point will be presented by treatment group within each cohort. The QTc will be calculated using both the Bazett and Fridericia corrections.

Electrocardiographic parameter values are considered PCI if they meet or exceed the higher-limit PCI criteria listed in Table C-5. The number and percentage of subjects with PCI postbaseline ECG values will be tabulated for each intervention period. The percentages will be calculated relative to the number of subjects with available non-PCI baseline values and at least 1 postbaseline assessment for the double-blind intervention period within the corresponding cohort. The numerator is the total number of subjects with available non-PCI baseline values and at least 1 PCI postbaseline value for the double-blind intervention period of the corresponding cohort. A supportive tabular display of subjects with PCI postbaseline values will be provided, including the PID number, baseline, all postbaseline (including non-PCI) values, and change from baseline. In this listing, any subject with PCI value (if any) during postintervention period will also be included.

In addition, a tabular display showing all AEs that occurred in subjects who had postbaseline PCI ECG values will be provided.

A shift table from baseline to the end of double-blind intervention period in the Investigator's overall interpretation of the ECG will be presented by treatment group within each cohort for the following categories: normal; abnormal, not clinically significant; abnormal, clinically significant. A tabular display showing subjects with postbaseline clinically significant ECG abnormalities according to the Investigator's overall interpretation will be provided.

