Appendix B. Variable Derivation

Missed eDiary Assessments

No imputation or derivation will be performed for missed eDiary assessments unless otherwise specified.

Incomplete eDiary Assessments

Missing responses in incomplete eDiary assessments will not be imputed for most of the parameters, with the exception of rescue medication (RM) use and BM frequency.

If the answer to the RM use question is missing in eDiary, no RM usage will be considered during that diary period in eDiary.

If the answer to the question related to BM frequency is missing in any daily eDiary, BM frequency will be considered as zero for that diary period in the eDiary.

Incomplete Clinic Diary on Enrollment/Randomization Visit

Missing responses in an incomplete clinic diary on enrollment/randomization day will be handled in a similar way as mentioned for incomplete daily eDiary assessments.

Stool frequency

Spontaneous Bowel Movement (SBM)

A SBM is a BM that occurs in the absence of laxative, suppository, or enema use on the calendar day of the BM or the calendar day before the BM.

Stool Frequency Rates

The components for calculating a subject's stool frequency rates (SBM weekly rates) for a given period are as follows:

- The number of BMs that occurred during that specific period

- The number of those BMs that were SBMs
- The number of days during that specific period:
- Enrollment/Randomization day will be considered as a half day for the double-blind intervention period and preintervention period.

Duration of an Analysis Week

With respect to a subject's scheduled analysis weeks, the term duration is used. In regard to the duration of a week, it is expected that 1 or more of a subject's "weeks" may not be exactly 7 days in duration (e.g., a subject may withdraw or discontinue early from the trial or may have missing diary day). Deviations from the 7 days norm are structural in nature; and, as such, the calculations of the weekly rates of SBMs will incorporate the actual days contributed within the time period (week or specific phase).

Weekly Stool Frequency Rate Calculations

The weekly frequency rate for SBMs will be based on the total number of SBMs reported by a caregiver as being directly observed by the caregiver based on the diary entries during that time period, adjusting for differences in the length of the time period. Weekly stool frequency rates for each specific period will be calculated as follows:

Weekly Frequency Rate (Specific Period) =

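### SAP 10.4 and 10.5 define the vital-sign and ECG PCI rates for the double-blind period only, and SAP 10.2.5 describes AESI more broadly than Protocol 6.1

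*SAP*

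**What the plan says.** **PCI rates.**

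- SAP 10.4: the number and percentage of subjects with PCI vital-sign values are "tabulated by treatment group for the double-blind intervention period separately". No open-label table is named, although the numerator is taken "during the specific period for the corresponding cohort".
- SAP 10.5 starts more widely: "The number and percentage of subjects with PCI postbaseline ECG values will be tabulated for each intervention period". The denominator, however, needs "at least 1 postbaseline assessment for the double-blind intervention period within the corresponding cohort". The numerator has the same restriction, and the shift table is described as "A shift table from baseline to the end of double-blind intervention period".
- SAP 6.3 (eDiary compliance) shows what the term means, listing "the open label period (Part 1), and the double-blind intervention period (Part 2") as separate periods. SAP 2.3 confirms that "Cohorts 1 to 3 will be open label with linaclotide only".
- SAP 10.1, the general rule for safety, covers both the open-label and the double-blind four-week periods. It asks for a summary of each Part 1 cohort and each Part 2 arm, with additional pooled summaries where cohorts share a dose.

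**AESI.**

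- SAP 10.2.5 describes AESI as significant volume depletion, significant electrolyte abnormality or ECG abnormality judged related to diarrhea. It plans counts and percentages by preferred term, and a listing. The AE overview in SAP 10.2.2 also has an AESI row.
- Protocol 6.1 requires, for all three types, that the event is clinically significant, due to diarrhea and related to study drug. Dehydration must also have led to hospitalization.
- SAP 14.1, the section for changes from the protocol's planned analyses, reports none.

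**The concern.** A programmer normally follows the specific section over the general one, and a percentage is fixed by its numerator and denominator. If both are confined to the double-blind period, the three open-label cohorts have no defined PCI rate for ECG and none at all for vital signs. Those cohorts hold most of the planned linaclotide experience. The vital-sign criteria in SAP Table C-4 include weight loss and postural changes in blood pressure and pulse, which are the findings one would look at for a drug whose main risk is diarrhea in children under two.

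The AESI point matters because AESI carries decisions in Part 1. One treatment-related AESI stops a cohort (Protocol 5.11), and absence of one is a condition for selecting a dose (Protocol 4.1). If the report counts AESI on a looser description than the one used for those decisions, a cohort that properly passed could appear to have had a stopping event.

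**Working it through.** The plan gives no figure of its own to reproduce here. The check compares the texts and then counts planned exposures.

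**1. Which rows have a defined rate?**

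| Output | Period named in its own section | SAP 10.1 | Lost on a literal reading |
|---|---|---|---|
| Vital-sign PCI n (%) (10.4) | Double-blind only | Part 1 cohorts, Part 2 arms, pooled same dose | Part 1 rows and pooled row |
| ECG PCI count (10.5) | Each intervention period | Same | Nothing |
| ECG PCI percentage (10.5) | Double-blind only, numerator and denominator | Same | Part 1 and pooled percentages |
| ECG shift table (10.5) | End of double-blind period | Same | Part 1 and pooled tables |
| Laboratory PCI n (%) (10.3) | Neutral assessment period | Same | Nothing |

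SAP 10.4 therefore conflicts with 10.1. SAP 10.5 conflicts with 10.1 and with its own opening sentence on PCI counts.

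**2. How much linaclotide experience is involved?** Inputs from Protocol 4.1: six children in each of Cohorts 1 to 3, and twelve in Part 2 randomized 1:1, so six on linaclotide.

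- Full enrollment: 3 × 6 + 6 = 24 linaclotide exposures. Outside the literal rate: 18/24 = 75%.
- Minimum of 18 enrolled, assumed to be one Part 1 cohort plus Part 2 (6 + 12 = 18): 6 + 6 = 12 linaclotide exposures. Outside: 6/12 = 50%.

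These are exposures. Children from Cohorts 1 and 2 may re-enter at a higher dose, so at full enrollment the number of distinct children can be lower.

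**3. What does one case look like at the selected dose?** Part 2 recruits new subjects, so the 6 + 6 = 12 children at that dose are distinct. Suppose one child in the Part 1 cohort has a PCI vital-sign value and none in the Part 2 linaclotide arm does.

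| Row | As SAP 10.1 intends | SAP 10.4 read literally |
|---|---|---|
| Part 1 cohort | 1/6 (16.7%) | Absent |
| Part 2 linaclotide | 0/6 (0%) | 0/6 (0%) |
| Pooled same dose | 1/12 (8.3%) | Absent |

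For ECG, the count of one could still be shown, but its percentage would have no defined denominator. Real denominators may be below six, because a non-PCI baseline and at least one postbaseline value are required.

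**4. How do the AESI descriptions differ?**

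| Criterion | SAP 10.2.5 | Protocol 6.1 |
|---|---|---|
| Linked to diarrhea | Yes | Yes |
| Related to study drug | Not required | Required, all types |
| Volume depletion or dehydration | Significant | Clinically significant and causing hospitalization |
| Electrolyte abnormality | Significant | Clinically significant |
| ECG abnormality | No significance threshold | Clinically significant |

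Every Protocol 6.1 event meets the SAP description, but not the reverse. The SAP text matches how Protocol 2.1 and 4.2 describe AESI in earlier linaclotide studies, which suggests it was carried over.

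Example: one child in a cohort of six has drug-related volume depletion, judged significant but treated without admission. Under the SAP wording this is 1/6 (16.7%); under Protocol 6.1 it is 0/6.

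**The case against.** The best defense on PCI is that the wording is left over from another plan and the intent is clear. SAP 10.1 governs all safety analyses. Part 2 is a single cohort, so the references to the corresponding cohort in 10.4 and 10.5 serve little purpose unless Part 1 is meant as well. Appendix B also uses the term loosely: "Enrollment/Randomization day will be considered as a half day for the double-blind intervention period and preintervention period", in a rule that must apply to Part 1 too. This stands as evidence of intent, but it does not repair a rate whose stated numerator and denominator say something else.

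Two stronger readings are tempting and do not hold. A reader might infer that Part 1 has no ECG PCI table at all; SAP 10.5 does tabulate the counts for each intervention period, so only the percentage and the shift table are affected. A reader might also infer that the Part 2 rate is distorted, with one Part 2 case shown as 1/6 in place of 1/12. Under SAP 10.1 the pooled summary is additional to the by-arm rows, so the Part 2 row is 1/6 on either reading.

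On AESI, the defense is that the sentence in 10.2.5 says what will be monitored and gives no counting algorithm. Sites apply Protocol 6.1, and the case report form is not among the documents, so the table may in practice use site-identified events. That is fair, and the example is conditional on the table following the SAP wording. Cohort stopping and dose selection also already specify treatment-related AESI, so the missing drug-relation criterion matters less for comparison with those rules. What remains is mainly hospitalization and clinical significance. The planned AE tables by relationship (SAP 10.2.3) cannot sort out hospitalization; the AESI listing has to do that.

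**Conclusion.** Both points are wrong as written, minor, and limited to reporting.

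For PCI, a literal reading loses the Part 1 vital-sign rows, the Part 1 ECG percentages and shift table, and the pooled same-dose rows. This touches 75% of planned linaclotide exposures at full enrollment, or 50% under the assumed composition of the 18-subject minimum. The calculation assumes cohorts and arms fill as planned.

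For AESI, the reported count can exceed the protocol's. A single non-admitted case moves a cohort of six from 0/6 to 1/6, provided that the table follows the SAP wording and the event is judged significant.

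A reader might infer that safety decisions are compromised. The documents do not support that: escalation, stopping and dose selection run under the protocol and the committee's review and do not depend on these tables. There is no hypothesis testing to distort. The displays of subjects with PCI values and the AESI listing still show every case.

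**What to change.** In SAP 10.4 and 10.5, at every place where the period is named (count, numerator, denominator, shift table), replace the double-blind intervention period with *the study intervention period, by cohort in Part 1 and by treatment group in Part 2, with pooled same-dose summaries in addition*.

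In SAP 10.2.5, use the Protocol 6.1 definition of AESI. Alternatively, keep the broader set, flag the events that meet Protocol 6.1 and tabulate those separately; in that case record the difference in SAP 14.1.

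The cost is wording in three SAP sections, or one extra AESI flag alongside the PCI rewording. No new data and no protocol change are needed.

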10.5 Other Safety Analyses

Electrocardiogram

Descriptive statistics for ECG parameters (ventricular heart rate, RR interval, PR interval, QRS interval, QT interval, and QTc) and changes from baseline values at each assessment time point will be presented by treatment group within each cohort. The QTc will be calculated using both the Bazett and Fridericia corrections.

Electrocardiographic parameter values are considered PCI if they meet or exceed the higher-limit PCI criteria listed in Table C-5. The number and percentage of subjects with PCI postbaseline ECG values will be tabulated for each intervention period. The percentages will be calculated relative to the number of subjects with available non-PCI baseline values and at least 1 postbaseline assessment for the double-blind intervention period within the corresponding cohort. The numerator is the total number of subjects with available non-PCI baseline values and at least 1 PCI postbaseline value for the double-blind intervention period of the corresponding cohort. A supportive tabular display of subjects with PCI postbaseline values will be provided, including the PID number, baseline, all postbaseline (including non-PCI) values, and change from baseline. In this listing, any subject with PCI value (if any) during postintervention period will also be included.

In addition, a tabular display showing all AEs that occurred in subjects who had postbaseline PCI ECG values will be provided.

A shift table from baseline to the end of double-blind intervention period in the Investigator's overall interpretation of the ECG will be presented by treatment group within each cohort for the following categories: normal; abnormal, not clinically significant; abnormal, clinically significant. A tabular display showing subjects with postbaseline clinically significant ECG abnormalities according to the Investigator's overall interpretation will be provided.

11.0 Other Analyses

Not applicable.

12.0 Interim Analyses

No Interim Analysis is planned.

12.1 Internal Dose Escalation Committee

In Part 1, an internal dose escalation review committee (IDERC) will be monitoring the safety of Cohorts 1-3 and will provide a recommendation for the dose escalation to the next cohort or to stop the study based on the overall benefit-risk profile.

12.2 Data Monitoring Committee

In Part 2, an external Data Safety Monitoring Board (DSMB) composed of persons independent of AbbVie and with relevant expertise in their field will review unblinded safety data from the ongoing study. The primary responsibility of the DSMB will be to protect the safety of the subjects participating in this study.

A separate DSMB charter describes the roles and responsibilities of the DSMB members, frequency of data reviews, relevant data to be assessed, and general operations.

13.0 Overall Type-I Error Control

There is no hypothesis testing for this study. No multiplicity adjustment will be applied.

14.0 Version History

Table 2. SAP Version History Summary

Version	Date	Summary
1.0	17 May 2023	Initial version

14.1 Changes to Planned Analyses in the Protocol

NA

Appendix B. Variable Derivation

Missed eDiary Assessments

No imputation or derivation will be performed for missed eDiary assessments unless otherwise specified.

Incomplete eDiary Assessments

Missing responses in incomplete eDiary assessments will not be imputed for most of the parameters, with the exception of rescue medication (RM) use and BM frequency.

If the answer to the RM use question is missing in eDiary, no RM usage will be considered during that diary period in eDiary.

If the answer to the question related to BM frequency is missing in any daily eDiary, BM frequency will be considered as zero for that diary period in the eDiary.

Incomplete Clinic Diary on Enrollment/Randomization Visit

Missing responses in an incomplete clinic diary on enrollment/randomization day will be handled in a similar way as mentioned for incomplete daily eDiary assessments.

Stool frequency

Spontaneous Bowel Movement (SBM)

A SBM is a BM that occurs in the absence of laxative, suppository, or enema use on the calendar day of the BM or the calendar day before the BM.

Stool Frequency Rates

The components for calculating a subject's stool frequency rates (SBM weekly rates) for a given period are as follows:

- The number of BMs that occurred during that specific period

- The number of those BMs that were SBMs
- The number of days during that specific period:
- Enrollment/Randomization day will be considered as a half day for the double-blind intervention period and preintervention period.

Duration of an Analysis Week

With respect to a subject's scheduled analysis weeks, the term duration is used. In regard to the duration of a week, it is expected that 1 or more of a subject's "weeks" may not be exactly 7 days in duration (e.g., a subject may withdraw or discontinue early from the trial or may have missing diary day). Deviations from the 7 days norm are structural in nature; and, as such, the calculations of the weekly rates of SBMs will incorporate the actual days contributed within the time period (week or specific phase).

Weekly Stool Frequency Rate Calculations

The weekly frequency rate for SBMs will be based on the total number of SBMs reported by a caregiver as being directly observed by the caregiver based on the diary entries during that time period, adjusting for differences in the length of the time period. Weekly stool frequency rates for each specific period will be calculated as follows:

Weekly Frequency Rate (Specific Period) =

$$\frac{\text{Total number of directly observed SBMs reported by a caregiver during the specific period}}{\text{Number of days during the specific period}} * 7$$

The weekly frequency rate for SBMs will also be derived based on the total number of SBMs occurring based on the diary entries during that time period (including SBMs not directly observed by the caregiver), adjusting for differences in the length of the time period.

Weekly Frequency Rate (Specific Period) including SBMs not directly observed by caregiver =

$$\frac{\text{Total number of SBMs during the specific period}}{\text{Number of days during the specific period}} * 7$$

Stool Consistency

The caregiver will be asked to rate the child's observed stool consistency for each BM the caregiver was present for using the Bristol Stool Form Scale (BSFS), a 7-point ordinal scale:

"Choose the option that is most like bowel movement X you were with the child for"

Type 1: Separate hard lumps, like nuts

Type 2: Sausage-shaped but lumpy

Type 3: Like a sausage, but with cracks on the surface

Type 4: Like a sausage or snake, smooth and soft

Type 5: Soft blobs with clear cut edges

Type 6: Fluffy pieces with ragged edges, a mushy stool

Type 7: Watery, no solid pieces.

I don't know.

A subject's stool consistency score for the study intervention period will be the average of the non-missing BSFS scores for the caregiver-observed SBMs during that specific period.

Straining

If the caregiver was present for the BM, the caregiver will be asked to rate the amount of straining observed when the child passed the BM using the following two 3-point rating scales. The caregiver will be asked to assess the degree of straining for every BM for which he/she was present by responding to the following two questions in the daily eDiary:

For the bowel movement X you were with the child for, did he/she grunt like he/she was straining?

- No, not at all
- Yes, a little
- Yes, a lot
- I don't know

For the bowel movement X you were with the child for, did he/she make a face like he/she was straining?

- No, not at all
- Yes, a little
- Yes, a lot
- I don't know

The subject's daily straining score for each caregiver-observed BM will be derived based on the average of non-missing responses of the two straining questions. The subject's straining score will be the average of the non-missing daily average straining scores for the caregiver-observed SBMs during the specific period.

Global Items

The global items consist of two items, one assessing global change in the child's symptoms and one assessing the global severity of the child's symptoms. Both global

items will be completed weekly on the eDiary by the caregiver. The global severity item will be completed beginning at the preintervention period through the study intervention period and the global change item will be completed beginning at one week after Enrollment/Randomization through the study intervention period.

Global Change Item

The global change item assesses the change in the child's constipation (1 item) as follows:

Please choose the response below that best describes the overall change in your child's constipation since he/she started taking the study medication.

- Much better
- A little better
- No change
- A little worse
- Much worse

Global Severity Item

The global severity item assesses the severity of the child's constipation (1 item) as follows:

How would you rate the severity of the child's constipation over the past 7 days?

- None
- Mild
- Moderate
- Severe
- Very severe

